4.2 Secondary clinical outcomes

Secondary end points were the presence of reflux symptoms (GerdQ score >7) or evidence of reflux esophagitis under endoscopy during follow-up. In addition, we will evaluate pathological differences between different sites to provide evidence for selecting the best biopsy site.

Data processing and analysis

Measurement data are expressed as $x \pm s$ or median, as appropriate,

and count data rate and percentage are expressed. The chi-square test or Fisher's exact test was used to analyze the count data, and the Student's T test or Mann-Whitney test was used to analyze the qualitative and quantitative differences among the subgroups. All P values were bilateral, and P <0.05 was considered as statistically significant difference.

Quality control

In this study, two doctors will participate in patient enrollment, input of baseline data and follow-up data, and jointly check the accuracy and authenticity of data.

References

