This study prospectively collects the information of 50 participants undergoing POEM for achalasia in Beijing Friendship Hospital, Capital Medical University. During POEM, all patients are required to obtain esophageal muscle biopsy for pathological examination. Participants will be followed up by telephone at 1, 3, 6, and 12 months after POEM for improvement in clinical symptoms.

Research proposal

1. Research design

This is a prospective study based on Beijing Friendship Hospital affiliated to Capital Medical University. The data of 50 patients undergoing POEM due to achalasia were prospectively collected,

including demographic data, drug and surgical treatment data during hospitalization. At POEM, all patients are required to obtain esophageal muscle biopsy and mucosal tissue samples for pathological examination. The patients were followed up by telephone at 1, 3, 6, and 12 months for improvement in clinical symptoms.

2. The research object

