3.1.2 Endoscopy

All patients underwent endoscopy to exclude tumors, inflammatory reactions or large ulcers in the esophagus and stomach, especially in the lower esophagus or the gastroesophageal junction.

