3.4 Follow-up contents

Follow-up data were collected, including symptom relief (Eckardt score), reflux symptom score (GerdQ score), gastroscopic manifestations, reflux esophagitis, esophagography and esophageal manometry. Follow-up collection time is 1 month, 3 months, 6 months and 12 months after POEM. Patients' symptom improvement and postoperative reflux will be inquired.

4. Clinical outcomes

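### Does follow-up by telephone leave the endoscopic part of the reflux end point without data?

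*Combined protocol and SAP*

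**What the plan says.** Four places bear on this.

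- **Research content** describes the follow-up contacts: "Participants will be followed up by telephone at 1, 3, 6, and 12 months after POEM for improvement in clinical symptoms". **Research design** repeats it: "The patients were followed up by telephone at 1, 3, 6, and 12 months for improvement in clinical symptoms".
- **Section 3.4, Follow-up contents**, gives the data items: "Follow-up data were collected, including symptom relief (Eckardt score), reflux symptom score (GerdQ score), gastroscopic manifestations, reflux esophagitis, esophagography and esophageal manometry". It then gives one set of times, without distinguishing items: "Follow-up collection time is 1 month, 3 months, 6 months and 12 months after POEM". It closes with a sentence about questioning: "Patients' symptom improvement and postoperative reflux will be inquired".
- **Section 4.2, Secondary clinical outcomes**, defines the reflux outcomes: "Secondary end points were the presence of reflux symptoms (GerdQ score >7) or evidence of reflux esophagitis under endoscopy during follow-up".
- **Section 3.1.2, Endoscopy**, is the only place that puts every patient through endoscopy, and it concerns diagnosis: "All patients underwent endoscopy to exclude tumors, inflammatory reactions or large ulcers in the esophagus and stomach".

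Section 2.2 sets enrolment at 50. Data processing and analysis names tests for counts and measurements, and says nothing about patients who lack a follow-up endoscopy.

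**The concern.** The Eckardt and GerdQ scores can be taken by telephone. Gastroscopic findings, reflux esophagitis, esophagography and manometry cannot; they come from three in-person tests. A reader who takes the telephone sentences as the whole of follow-up would expect no endoscopies. A reader who applies the four times in section 3.4 to every item would expect one per patient at each time. Two people could follow the text faithfully and collect different reflux data.

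The stakes depend on how section 4.2 is read. If it names two end points, GerdQ is safe, but esophagitis could rest on anything from none to all 50 patients. If it names one composite, a patient reached only by telephone can be classed positive on GerdQ but never negative, because a negative result needs an endoscopy. The composite rate could then be pushed down or up according to how undetermined patients are treated.

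**Working it through.** The documents give no reflux figure to reproduce. The check is a comparison of the text, followed by an illustration.

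**1. Can the sections be read together?** Both telephone sentences state a purpose, symptom improvement, and neither says that calls are the only contact. Section 3.4 lists test results among the data gathered, and section 4.2 relies on one of them. Calls for symptoms, with test results collected as they become available, satisfies all of these sections. Section 4.2 also asks for esophagitis at some time during follow-up, so a single endoscopy can meet the definition.

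**2. How wide are the literal extremes?** With 50 patients and 4 times, 50 × 4 = 200 endoscopies, and with three tests 200 × 3 = 600 in-person tests. The telephone sentences alone supply 0. Neither extreme is a fair reading: the upper one applies every time to every item, and the lower one ignores sections 3.4 and 4.2. The gap between them does not measure any effect.

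**3. Two end points, the reading that the plural in section 4.2 fits.** GerdQ is unaffected. For esophagitis the cost is precision. Assume a rate of 30% (the documents give none) and use Wilson 95% intervals:

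| Patients examined | Events | 95% interval |
|---|---|---|
| 50 | 15 | 19-44% |
| 20 | 6 | 15-52% |
| 10 | 3 | 11-60% |

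**4. One composite.** Let g be the share with GerdQ above 7, q the esophagitis rate, and s the share of GerdQ-negative patients examined. Assume g = 0.20, q = 0.30, GerdQ and esophagitis independent, and examination unrelated to esophagitis.

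- True rate: 1 − (1 − g)(1 − q) = 1 − 0.80 × 0.70 = 0.44.
- Undetermined at s = 0.4: 0.80 × 0.60 = 0.48, or 24 of 50.
- Undetermined counted as negative: g + (1 − g)sq = 0.20 + 0.80 × 0.4 × 0.30 = 0.296.
- Undetermined excluded: 0.296 / (0.20 + 0.80 × 0.4) = 0.296 / 0.52 = 0.569.
- At s = 0.8 the same two handlings give 0.392 and 0.467. At s = 0 they give 0.20 and 1.00, with 40 of 50 undetermined.
- Over g from 0.15 to 0.25 and q from 0.20 to 0.40, at s = 0.4, the errors are 9 to 20 points too low or 9 to 16 points too high.

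These errors come from two crude handlings, neither of which the plan prescribes. Using the esophagitis rate among examined GerdQ-negative patients gives g + (1 − g)q = 0.20 + 0.80 × 0.30 = 0.44, the true value, at any s above zero. If uptake is the same in GerdQ-positive and GerdQ-negative patients, analysing only examined patients also gives 0.44.

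**The case for a change.** The best case for a change is that nobody can tell from the text who will have a follow-up endoscopy. The test items share the four times of the calls, section 3.4 ends by describing questioning, and no in-person visit is named. A published esophagitis rate is hard to interpret unless the reader knows how many patients were examined and why. A sentence or two and a few form items would cost little.

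Part of this stands. The schedule is unspecified, section 4.2 does not say outright whether it means one end point or two, and the report should give the number examined. But this is detail that the study team supplies in any event. The study is at one hospital, and under Quality control two doctors enter the follow-up data and check it jointly, so divergent practice between sites does not arise.

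More wording would not repair the one real risk either. If patients are examined because they have symptoms, the esophagitis rate is selected whether or not the plan says so. The illustration assumes that selection away, and recording unexamined patients as not assessed would disclose it without removing it. Declaring the two components separate would only restate what the plural already suggests or, if a composite was intended, would redefine the outcome.

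**Conclusion.** This is missing detail about a secondary outcome, and no change to the plan is needed. The telephone sentences and section 3.4 are compatible, and section 4.2 can be met by one endoscopy at any time in follow-up. Nothing in the plan makes an unexamined patient a negative.

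The primary Eckardt outcome is unaffected. On the likelier two-end-point reading the only quantified cost is a wider interval for esophagitis, from 19-44% with 50 examined to 11-60% with 10, at an assumed rate of 30%. On the composite reading the 9 to 20 point errors arise only under handlings that the plan does not adopt. The recovery of 44% assumes that some GerdQ-negative patients are examined and that examination is unrelated to esophagitis among them. No effect on comparisons between pathology groups has been shown. The ordinary analysis, esophagitis among patients examined with that number as the denominator, is sufficient.

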2.3 Into the discharge standard

Inclusion criteria:

- 1) Patients with achalasia treated in Beijing Friendship Hospital, Capital Medical University
- 2) Age 18-80, no gender limitation
- 3) Fit and agree to receive POEM therapy
- 4) Signed informed consent

Exclusion criteria:

- 1) the previously received treatment of achalasia, Barrett's esophagus lesions, esophageal stricture, liver cirrhosis, and/or

esophageal varices, the digestive tract tumor, active esophagitis, connective tissue disease, allergic disease, blood or blood coagulation patients and hiatal hernia.

2) Use of nonsteroidal anti-inflammatory drugs, corticosteroids, or other immunosuppressive drugs 6 months prior to examination.

3. Research methods

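### The secondary reflux end point takes no account of acid-suppressing drugs, and the plan states no way to identify patients whose reflux after POEM was suppressed by treatment before any positive assessment.

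*Combined protocol and SAP*

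**What the plan says.** The secondary outcome in section 4.2 is "Secondary end points were the presence of reflux symptoms (GerdQ score >7) or evidence of reflux esophagitis under endoscopy during follow-up". It sets no condition on whether the patient is on or off acid suppression when assessed.

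Drug information is mentioned under Research proposal, 1. Research design, where the data collected are described as "including demographic data, drug and surgical treatment data during hospitalization".

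Section 3.4 gives the follow-up items: "Follow-up data were collected, including symptom relief (Eckardt score), reflux symptom score (GerdQ score), gastroscopic manifestations, reflux esophagitis, esophagography and esophageal manometry". The timing is "Follow-up collection time is 1 month, 3 months, 6 months and 12 months after POEM", and the section adds that "Patients' symptom improvement and postoperative reflux will be inquired". No item concerns medication.

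The only drug classes named anywhere are those in the second exclusion criterion of section 2.3: "Use of nonsteroidal anti-inflammatory drugs, corticosteroids, or other immunosuppressive drugs 6 months prior to examination". Acid-suppressing drugs are not mentioned in any section.

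For the analysis of binary outcomes, the section Data processing and analysis states: "The chi-square test or Fisher's exact test was used to analyze the count data". It names no covariate, stratum or sensitivity analysis.

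**The concern.** Acid suppression is given to relieve reflux symptoms and to heal esophagitis, and these are the two components of the end point. Take two patients with the same reflux after POEM. One starts a drug soon after discharge and is at or below GerdQ 7 with no esophagitis whenever assessed; the other is untreated and crosses a threshold. The first is a non-event and the second an event. The plan states nothing that would let the analyst recognise the first patient.

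The study asks whether outcome after POEM differs between pathology groups. If drug use removes events in the same proportion in every group, the reflux rate is too low and a real association is diluted. If the proportion differs between groups, the comparison partly reflects who was treated. Drug use that is not asked about during the 12 months is hard to reconstruct afterwards.

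**Working it through.** **Step 1. Is there a figure to reproduce?** No. The plan gives 50 patients but no reflux rate, drug-use rate, group sizes or power. The check is therefore one of text, followed by an illustration on assumed rates.

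**Step 2. Who is misclassified?** Section 4.2 joins its two components with *or* and applies them *during follow-up*, so one positive finding at any time most naturally makes the patient an event. A patient with reflux is masked only if both conditions hold:

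- treatment began before any positive assessment, for example at discharge or between contacts; and
- the GerdQ score stayed at 7 or below and no esophagitis was seen at every later assessment.

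A patient who scores above 7 at month 1 and is then treated has already counted.

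**Step 3. Effect on the observed rate.** Let *p* be the true proportion with reflux and *m* the share of them masked in the sense of Step 2. Then

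observed rate = *p* × (1 − *m*).

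With *p* = 40% (assumed):

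- Half treated, and half of those suppressed: *m* = 0.5 × 0.5 = 0.25. Observed rate 0.40 × 0.75 = 30%.
- 80% treated, and 70% of those suppressed: *m* = 0.8 × 0.7 = 0.56. Observed rate 0.40 × 0.44 = 17.6%.

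Events counted among 50 patients over a wider assumed range:

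| True rate | True events | *m* = 0 | *m* = 25% | *m* = 50% | *m* = 75% |
|---|---|---|---|---|---|
| 20% | 10 | 10 | 7.5 | 5.0 | 2.5 |
| 30% | 15 | 15 | 11.25 | 7.5 | 3.75 |
| 40% | 20 | 20 | 15 | 10 | 5 |
| 50% | 25 | 25 | 18.75 | 12.5 | 6.25 |

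The formula does not model repeated assessments. If *m* is guessed from treatment and suppression rates at one time point, as in the two bullets above, it overstates masking, because it ignores events recorded before treatment.

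**Step 4. Equal masking in two pathology groups.** Assume 25 patients per group and true rates of 50% and 20%. Power is by the normal approximation to the chi-square test, two-sided 0.05:

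power = Φ[(|*p*₁ − *p*₂| − 1.96 × SE₀) / SE₁],

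with SE₀ from the pooled rate and SE₁ from the separate rates.

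| *m* in both groups | Observed rates | Power |
|---|---|---|
| 0 | 50% vs 20% | 0.61 |
| 25% | 37.5% vs 15% | 0.44 |
| 50% | 25% vs 10% | 0.28 |
| 75% | 12.5% vs 5% | 0.15 |

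Fisher's exact test gives lower values at this size; the direction is the same.

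**Step 5. Unequal masking.**

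- *A difference created.* True rates 40% in both groups, *m* = 50% in one and 10% in the other: 0.40 × 0.50 = 20% against 0.40 × 0.90 = 36%. This is a spurious gap of 16 points. By the same approximation, the chance of p < 0.05 is about 0.24 instead of 0.05.
- *A difference hidden.* True rates 50% and 20%, *m* = 60% in the first group and 0 in the second: 0.50 × 0.40 = 20% against 20%.

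The bias can therefore go either way.

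**The case against.** **The lists are not closed.** Both the list of data collected and the list of follow-up items are introduced by *including*, and asking about reflux at follow-up could extend to its treatment. The documents contain no case report form. This stands as far as it goes. A reader might infer that drug use after discharge will certainly not be collected, or that treated and untreated patients cannot be told apart; the text supports only that the plan specifies no such item and no way to tell them apart. Even if an unseen form holds the data, no definition or analysis in the plan uses them.

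**GerdQ may itself reflect some drug use.** The documents do not reproduce its items, so this cannot be settled here. A total score cut at 7 would in any case not record the drug, its timing or its reason.

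**Early positives already count.** This is correct, and it narrows the problem to the patients described in Step 2. A reader might infer that the patients with the worst reflux are moved into the no-reflux group. That does not follow for anyone recorded positive before treatment.

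**Reflux under usual care is a legitimate outcome.** This also stands, and it is a reason to keep the end point as written. It does not remove the need to know how much of the observed absence of reflux occurs on treatment.

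**Only a secondary outcome is affected.** Agreed. Poor prognosis is defined by the Eckardt score in section 4.1, and nothing here bears on it.

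**Conclusion.** The point holds as a gap in specification. The reflux end point ignores acid suppression, the plan names drug data only for the hospital stay, and the follow-up items include no medication. Patients treated before any positive assessment and suppressed throughout are classed as free of reflux, with no stated means of identifying them.

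The size is unknown. The fall from 40% to between 30% and 17.6% is correct arithmetic on assumed rates, and less masking is expected because early positives count. A reader might take the corresponding 5 to 11 lost events out of 20 (20 × 0.25 = 5; 20 × 0.56 = 11.2) as an estimate or a bound for this study. It is neither, since every input is assumed and the calculation does not model repeated assessments. A reader might also infer that the only effect is to weaken an association with pathology. That needs equal masking across groups, which the documents do not establish; unequal masking can create a difference or hide one.

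The conclusion rests on the plan as written being the whole specification, and on acid suppression being able to bring some patients below both thresholds. It is a cheap improvement to a secondary outcome.

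**What to change.** - **Section 3.4:** add current acid-suppressing drug use (yes or no) and its reason (reflux symptoms or routine) at 1, 3, 6 and 12 months. Record the same at any follow-up endoscopy, because esophagitis is read there and not on the telephone.
- **Section 4.2:** keep the end point as defined for the main reflux analysis, and state that it is counted whether or not the patient is on acid suppression.
- **Data processing and analysis:** add one sensitivity analysis in which drug use for reflux symptoms also counts as an event. Routine use alone does not count.
- **Reporting:** tabulate drug use by pathology group descriptively. Do not test reflux within strata of drug use: use after POEM is itself driven by reflux, and the strata would be sparse with 50 patients.

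The cost is one extra question per existing contact and one extra table. The sensitivity analysis may over-count events if the reason for use is misreported, so it should be read beside the main result and not in place of it. No change to treatment, visits or sample size is proposed.

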Study Protocol and Statistical Analysis Plan

**Study on the Relationship Between Pathological
Features of Achalasia and Prognosis of Per-oral
Endoscopic Myotomy**

**Main research institute: Beijing Friendship Hospital,
Capital Medical University**

Study Director: [name],

Date: April 1st, 2021

Directory

1. Background	3
2. Research objectives	4
3. Research content	4
4. Research proposal	4
5. Data processing and analysis	9
6. Quality control	9
7. References	9

Background

Achalasia is the most common motility disorder of esophagus, characterized by disorders of the lower esophageal sphincter (LES). Normal peristalsis of the esophagus is eliminated and replaced by synchronous or ineffective contraction. Based on high-resolution manometry (HRM), the patients with achalasia were categorized into 3 subtypes, type I: achalasia with minimum esophageal pressurization, type II: achalasia with esophageal compression and type III: achalasia with spasm.

Previous studies have found that the pathological features of the esophageal muscular layers in patients with achalasia are degeneration of nerve plexus, reduction of interstitial cells of Cajal (ICCs), muscular atrophy, fibrosis and infiltration of different inflammatory cells. Different subtypes of achalasia have different clinical characteristics and esophageal motility. Studies have found that ganglion cells in type I patients are significantly reduced compared with type II patients, but the pattern is similar, which may indicate that type I achalasia represents the progression of type II achalasia. Studies have shown that ICCs are preserved in type III achalasia compared with type I and II achalasia. In addition, Achalasia is related to viral infection and autoimmune disease. Nowadays, per-oral endoscopic myotomy (POEM) is a main therapy for patients with achalasia. Most studies have focused on the relationship

between pathological features and motility characteristics of achalasia, but there are few studies on the relationship between pathological features and therapeutic effect of POEM.

This study will evaluate the pathological characteristics of full-thickness esophageal muscle in patients with achalasia in order to discover the relationship between different pathological characteristics and prognosis of POEM.

Research objective

To determine whether there is difference in prognosis of POEM among patients with achalasia of different pathological characteristics.

Research content

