3.2 POEM and muscular pathology

Patients received routine POEM surgery, and full-thickness esophageal muscle biopsy was performed from LES, distal esophagus (about 5cm above EGJ) and middle esophagus (about 10-20cm above EGJ) during the operation. Intraoperative biopsy to take pathological tissue depends on the patient's condition, and the collection method is to use biopsy forceps to take tissue, and take 1 piece at one place.

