3.3.1 Specific dyeing items

- 1) HE staining is used to evaluate the atrophy degree of smooth muscle and the number of inflammatory cells.
- 2) Azan-Mallory staining was used to assess the degree of fibrosis.
- 3) C-KIT immunohistochemistry: C-KIT was positive, and trypsin-like IHC staining was negative to evaluate ICC cells.
- 4) S100: Evaluate the degree of ganglion loss
- 5) The number of eosinophil cells was evaluated by HE staining, MBP

and EDN

- 6) Mast cells: C-kit positive, trypsin-like IHC staining positive.
- 7) Lymphocyte inflammation.

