4.1 Main clinical outcomes

The primary end point event of patients is Eckardt score in 1 month, 3 months, 6 months and 12 months after POEM. Any Eckardt score >3 points are defined as poor prognosis after POEM.

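### Any two-sided P<0.05 counts as significant across seven or eight overlapping pathological features, with no lead feature, multiplicity control or exploratory label

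*Combined protocol and SAP*

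**What the plan says.** The research objective is a single question: "To determine whether there is difference in prognosis of POEM among patients with achalasia of different pathological characteristics". Section 4.1 supplies the outcome: "Any Eckardt score >3 points are defined as poor prognosis after POEM".

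Section 3.3.1 lists seven staining items covering up to eight features: smooth-muscle atrophy, inflammatory cells in general, fibrosis, interstitial cells of Cajal (ICC), ganglion loss, eosinophils, mast cells and lymphocytes. The count is seven if the general inflammatory-cell item is not kept separate from the specific cell types. The features overlap. One HE item serves two purposes: "HE staining is used to evaluate the atrophy degree of smooth muscle and the number of inflammatory cells". ICC and mast cells are both read from c-KIT, split by a second stain: "C-KIT immunohistochemistry: C-KIT was positive, and trypsin-like IHC staining was negative to evaluate ICC cells" and "Mast cells: C-kit positive, trypsin-like IHC staining positive".

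Tissue comes from up to three levels (section 3.2): "full-thickness esophageal muscle biopsy was performed from LES, distal esophagus (about 5cm above EGJ) and middle esophagus (about 10-20cm above EGJ) during the operation". No level is named as the one for the prognosis analysis. Section 4.2 instead makes the choice of site a question for this study: "we will evaluate pathological differences between different sites to provide evidence for selecting the best biopsy site".

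The section on data processing and analysis allows chi-square or Fisher tests for count data and t or Mann-Whitney tests for subgroup differences. It then closes with one threshold for everything: "All P values were bilateral, and P <0.05 was considered as statistically significant difference". Neither that section nor any other ranks the features, adjusts for their number, or labels the tests exploratory.

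**The concern.** With one question and several features that can each answer it, a 5% threshold per feature does not give a 5% chance of a wrong answer to the question. One chance result among seven or eight features, in 50 patients, could be reported under this plan as a significant pathological predictor of POEM outcome. That affects the study's only stated objective. The plan gives no basis for deciding in advance how much weight such a result should carry.

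**Working it through.** **Inputs from the plan.** Two-sided 0.05 per test; t, Mann-Whitney, chi-square or Fisher tests (data processing and analysis); k = 7 or 8 features (section 3.3.1); 50 patients (section 2.2); one outcome per patient, any Eckardt score above 3 (section 4.1).

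**Assumed, because the plan does not give them.** A common correlation r between features of 0 to 0.9; 5 or 10 poor outcomes among 50 (also 8 for the 2x2 tests); one value per feature per patient. The plan states no overall error rate and no power, so it has no figure of its own to reproduce.

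**1. Independent features.** Chance of at least one P<0.05 when none is prognostic = 1 - 0.95^k.
- k = 7: 1 - 0.95^7 = 0.302
- k = 8: 1 - 0.95^8 = 0.337

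**2. Correlated features.** With an equicorrelated normal model, the chance is 1 - ∫ φ(u) {Φ[(1.96 - √r·u)/√(1-r)] - Φ[(-1.96 - √r·u)/√(1-r)]}^k du. The simulated columns use 50 patients, 5 or 10 poor outcomes and 10,000 runs per setting, and give the range over t, Mann-Whitney, and Mann-Whitney on 0-3 grades.

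| r | k = 7, formula | k = 7, simulated | k = 8, formula | k = 8, simulated |
|---|---|---|---|---|
| 0 | 0.302 | 0.283-0.305 | 0.337 | 0.315-0.342 |
| 0.5 | 0.230 | 0.223-0.236 | 0.250 | 0.242-0.256 |
| 0.7 | 0.178 | 0.175-0.188 | 0.191 | 0.190-0.202 |
| 0.9 | 0.114 | 0.109-0.125 | 0.119 | 0.114-0.133 |

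**3. Dichotomised features.** The true size of one 2x2 test follows from the hypergeometric distribution. The splits were 25/25, 20/30, 15/35 and 10/40, with 5, 8 or 10 poor outcomes. Eight independent tests give 1 - (1 - size)^8.

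| Test | Size of one test | At least one of eight |
|---|---|---|
| Fisher | 0-0.0488 | 0-0.33 |
| Chi-square, continuity-corrected | 0-0.0240 | 0-0.18 |
| Chi-square, uncorrected | 0.0073-0.0864 | 0.06-0.52 |

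For example, Fisher on a 25/25 split with 10 poor outcomes has size 0.0106, so 1 - (1 - 0.0106)^8 = 0.082. With 5 poor outcomes it can never reach P<0.05.

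**4. What Benjamini-Hochberg at 5% does.**
- When no feature is prognostic, the chance of any claim is about 2-5% (t and Mann-Whitney settings of step 2).
- When three of eight features truly differ by 1.0 SD (10 poor outcomes, t tests), the chance of at least one false claim is about 9-10% at r = 0, 7% at r = 0.5 and 4% at r = 0.9. The method controls the false discovery rate, not the chance of any false claim.

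**5. Its cost in power.** For one feature differing by 1.0 SD, the t-test noncentrality is √(n1·n2/(n1+n2)).
- 10 v 40: √(400/50) = 2.83; critical t on 48 df = 2.01; unadjusted power 0.79
- 5 v 45: √(225/50) = 2.12; unadjusted power 0.55

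Simulated power after Benjamini-Hochberg over eight features is about 0.50 and 0.25. Over seven it is about 0.52 and 0.26.

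**The case against.** The best defence is that this is discovery work. The Background ends by saying that the study aims to discover a relationship, and notes that little has been published on it. It is a single-centre cohort of 50 with no power calculation and no named hypothesis. Many statisticians would not adjust for multiplicity here, and since every stain is listed, a careful reader can count the features and discount accordingly. Nothing says that only significant features will be reported. Much of this stands, and it is why the main remedy is a label with full reporting rather than a mandatory correction. It does not remove the point: the objective is worded as a determination, and the significance rule has no qualifier.

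A reader might infer that the plan has a one-in-three false-positive rate. The documents do not support that. The 34% figure needs eight independent features, and section 3.3.1 shows that they overlap. It also applies only to t or Mann-Whitney tests. Atrophy, fibrosis and ganglion loss are described by degree and could be analysed as categories, where Fisher's test can bring the rate down to 0.

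A reader might also multiply by three biopsy sites. That gives 21-24 tests and 1 - 0.95^21 = 66% to 1 - 0.95^24 = 71% if all were independent. The plan does not say that each site will be tested against prognosis, and sites within a patient are unlikely to be independent.

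The count of one test per feature is itself a reading of section 4.1. Its first sentence names the Eckardt score at four visits as the primary endpoint, and only the second gives the single dichotomy used here.

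**Conclusion.** The concern holds in a limited form. As written, the plan would call a feature significant on an unadjusted P<0.05, with seven or eight candidates and none put first. With one t or Mann-Whitney test per feature and no true association, the chance of at least one such result is about 11-13% at r = 0.9 and 22-26% at r = 0.5, with an upper bound of about 34%. That is roughly two to seven times the nominal 5%. With dichotomised features no single figure applies, and the rate may lie below or well above 5%. The correlation, the number of poor outcomes and one value per patient are assumptions; only the number of features and the threshold come from the documents.

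It does not follow that Benjamini-Hochberg must be the sole basis for every statement. With power falling from about 0.79 to 0.50, that is a trade-off for the sponsor. What is needed is that the plan says what an unadjusted P<0.05 may be taken to mean.

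**What to change.** In the data processing and analysis section, replace the blanket threshold for the feature-prognosis comparisons with text to this effect:

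- These tests are exploratory.
- Every section 3.3.1 feature is reported against the section 4.1 outcome (any Eckardt score above 3), with its unadjusted estimate, 95% confidence interval and P value, plus a Benjamini-Hochberg adjusted P value across the family.
- No feature is described as an established predictor on an unadjusted P<0.05 alone.
- Comparisons by biopsy site, by visit, and for GerdQ and reflux esophagitis are exploratory too.

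If the sponsor wants a confirmatory claim, there are two routes. One is to name a single lead feature at a single biopsy site before outcomes are seen and test it at 0.05. The other is to base claims on the adjusted P values, accepting the power loss shown above and stating that the false discovery rate is what is controlled.

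The main fix needs no new data. Its cost is a little extra reporting, and that no feature can be claimed as confirmed from this study.
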